8.2.2 Vital Signs

Vital signs, including heart rate, respiratory rate, pulse oximetry, BP, and body temperature, will be performed as specified in the SoA (Section 1.3). The participant should be resting prior to the collection of vital signs.

Situations in which vital sign results should be reported as AEs are described in Section 8.3.7.

8.2.3 Electrocardiograms

A triplicate 12-lead ECG will be performed at time points specified in the SoA (Section 1.3). A 12-lead safety ECG will be obtained after 5 minutes' supine rest, using the sites' own ECG machines.

A pediatrician will judge the overall interpretation as normal or abnormal. If abnormal, it will be documented as to whether or not the abnormality is clinically significant by the Investigator. For neonates, ECGs must be evaluated by a physician who is experienced in reading neonatal ECGs. For all abnormalities (regardless of clinical significance), the specific type and nature of the abnormality will be documented. Clinically significant findings should also be documented on the AE page of the eCRF, if applicable.

The Investigator may add extra 12 lead resting ECG safety assessments if there are any abnormal findings or if the Investigator considers it is required for any other safety reason. These assessments should be entered as an unscheduled assessment.

All ECG readings will be digitally stored as source documents.

8.2.4 Clinical Safety Laboratory Assessments

Blood and urine samples for determination of clinical chemistry, hematology, coagulation, and urinalysis will be taken at the visits indicated in the SoA (Section 1.3).

Additional safety samples may be collected if clinically indicated at the discretion of the Investigator. The date, time of collection and results (values, units, and reference ranges) will be recorded on the appropriate eCRF.

The clinical chemistry, hematology, urinalysis, and coagulation will be performed at a central laboratory. Instruction for the collection and handling of the samples will be provided in the study-specific Laboratory Manual.

The following laboratory variables will be measured.

8.2.4.1 Hematology

Hematology	
White blood cell (WBC) count	Neutrophils absolute count
Red blood cell (RBC) count	Lymphocytes absolute count
Hemoglobin (Hb)	Monocytes absolute count
Hematocrit (HCT)	Eosinophils absolute count
Mean corpuscular volume (MCV)	Basophils absolute count
Mean corpuscular hemoglobin (MCH)	Platelets
Mean corpuscular hemoglobin concentration (MCHC)	

8.2.4.2 Serum Clinical Chemistry

Serum Clinical Chemistry	
Sodium	Alkaline phosphatase (ALP)
Potassium	Alanine aminotransferase (ALT)
Urea	Aspartate aminotransferase (AST)
Creatinine	Gamma glutamyl transpeptidase (GGT)
Albumin	Total bilirubin (TBL)
Calcium	Unconjugated bilirubin
Phosphate	Conjugated bilirubin
Glucose	Creatine Kinase

8.2.4.3 Urinalysis

Urinalysis	
Glucose	
Protein	
Blood	
Microscopy (if positive for protein or blood):	RBC, WBC, Casts (Cellular, Granular, Hyaline)

8.2.4.4 Coagulation Tests

Coagulation Tests	
International normalized ratio (INR)	
Activated partial thrombin time (aPTT)	
Prothrombin Time (PT)	

8.2.4.5 Pregnancy Testing

Pregnancy test (Females of Childbearing Potential)	
Serum human-beta chorionic gonadotrophin (screening)	Urine human-beta chorionic gonadotrophin (screening)

8.3 Adverse Events and Serious Adverse Events

The Investigator is responsible for ensuring that all staff involved in the study are familiar with the content of this section.

The definitions of an AE or SAE can be found in [Appendix B](#).

Adverse events will be reported by the participant (or, when appropriate, by a caregiver, surrogate, or the participant's legally authorized representative).

The Investigator and any designees are responsible for detecting, documenting, and recording events that meet the definition of an AE.

8.3.1 Time Period and Frequency for Collecting AE and SAE Information

Adverse events will be collected from the time of IMP administration throughout the study, up to and including the last visit. After IMP administration on Day 1, participants will be monitored on site for a minimum of one hour for general safety, including injection/infusion site reactions and hypersensitivity reactions (including anaphylaxis).

Serious adverse events will be recorded from the time of signing of the ICF throughout the study, up to and including the last visit.

If the Investigator becomes aware of an SAE with a suspected causal relationship to the IMP that occurs after the end of the clinical study in a participant treated by him or her, the Investigator shall, without undue delay, report the SAE to the Sponsor.

8.3.2 Follow-up of AEs and SAEs

Any AEs that are unresolved at the participant's last visit in the study are followed up by the Investigator for as long as medically indicated, but without further recording in the eCRF. AstraZeneca retains the right to request additional information for any participant with ongoing AE(s)/SAE(s) at the end of the study, if judged necessary.

Adverse Event Variables

The following variables will be collected for each AE:

- AE diagnosis and description (verbatim)
- The date and time when the AE started and stopped

- Severity grade/maximum severity
- Whether the AE is serious or not
- Investigator causality rating against the IMP(s) (yes or no)
- Action taken with regard to the IMP(s)
- AE caused participant to withdraw from study (yes or no)
- Outcome

In addition, the following variables will be collected for SAEs:

- Date AE met criteria for SAE
- Date Investigator became aware of SAE
- AE is serious due to
- Date of hospitalization (if hospitalized)
- Date of discharge
- Probable cause of death (if death occurred)
- Date of death (if death occurred)
- Autopsy performed (if death occurred)
- Causality assessment in relation to study procedure(s)
- Causality assessment to other medication

The following severity ratings will be used, adapted from the Common Terminology Criteria for Adverse Events version 5.0 ([NIH 2017](#)):

- Grade 1: An event of mild intensity that is usually transient and may require only clinical or diagnostic observations. The event does not generally interfere with usual activities of daily living.
- Grade 2: An event of moderate intensity that is usually alleviated with additional, specific therapeutic intervention, which is minimal, local, or non-invasive. The event interferes with usual activities of daily living, causing discomfort, but poses no significant or permanent risk of harm to the participant.
- Grade 3: A severe event that requires intensive therapeutic intervention but is not immediately life-threatening. The event interrupts usual activities of daily living, or significantly affects the clinical status of the participant.
- Grade 4: An event, and/or its immediate sequelae, that is associated with an imminent risk of death and urgent intervention is indicated.
- Grade 5: Death, as result of an event.

It is important to distinguish between serious and severe AEs:

- Severity is a measure of intensity, whereas seriousness is defined by the criteria in [Appendix B 2](#).
- An AE of severe intensity need not necessarily be considered serious. For example, nausea that persists for several hours may be considered severe nausea, but not a SAE. On the other hand, a stroke that results in only a limited degree of disability may be considered a mild stroke but would be an SAE.

8.3.3 Causality Collection

The Investigator should assess causal relationship between IMP and each AE, and answer ‘yes’ or ‘no’ to the question ‘Do you consider that there is a reasonable possibility that the event may have been caused by the IMP?’

For SAEs, causal relationship should also be assessed for other medication and study procedures. Note that for SAEs that could be associated with any study procedure the causal relationship is implied as ‘yes’.

A guide to the interpretation of the causality question is found in [Appendix B](#).

8.3.4 Adverse Events of Special Interest

Adverse events of special interest will be collected according to the time points specified in the SoA (Section 1.3).

Adverse events of special interest are events of scientific and medical interest, specific to the further understanding of the IMP safety profile, and require close monitoring and rapid communication by the Investigators to the Sponsor. An AESI can be serious or non-serious. All AESIs will be recorded in the eCRF. Serious AESIs will be recorded and reported as per Section [8.3.9](#). See also the AZD7442 IB, for additional information on AESIs.

Adverse events of special interest for AZD7442 are listed below. They include:

- Anaphylaxis and other serious hypersensitivity reactions, including immune complex disease ([Section 8.3.4.1](#)).
- Injection site and infusion site reactions ([Section 8.3.4.2](#)).
- MIS-C ([Section 8.3.4.3](#))
- Thrombotic events, heart failure, and cardiac ischemia ([Section 8.3.4.4](#))

8.3.4.1 Anaphylaxis and Hypersensitivity Reactions

The definition and management of anaphylaxis and serious hypersensitivity reactions are provided in [Appendix F](#). After IMP administration, participants will be monitored for at least one hour for general safety, including anaphylaxis and other hypersensitivity reactions (Section [8.3.1](#)).

8.3.4.2 Injection and Infusion Site Reactions

An injection/infusion site inspection will be performed on Day 1 and at any in-person visits up to and including Day 6 (see SoA in Section [1.3](#) and [Table 15](#)). If evidence of injection or infusion site reaction persists, the site will be rechecked at each visit until no evidence of an active reaction remains. The inspection will include assessment of size, redness/erythema, swelling, itching/pruritis, pain or tenderness, induration, discoloration). Any injection/infusion site reaction will be recorded as an AE and a photograph taken, at the discretion of the Investigator, with visible measuring tape.

Table 15 Injection/infusion Site Inspection

Procedure/time after injections or infusions have been administered	Immediately after IMP administration	30 minutes (\pm 10 minutes)	Immediately prior to participant release
Visual inspection of site	X	X	X
Palpation of site	X	X	X
Participant will be asked:			
Are you experiencing any discomfort?	X	X	X
If yes, has the feeling of discomfort changed since you received the injection?	NA	X	X

IMP, investigational medicinal product; NA, not applicable.

Any AEs should be reported as described in Section [8.3](#).

8.3.4.3 Multisystem Inflammatory Syndrome - Children

For this study, MIS-C is defined as follows ([CDC 2021d](#)):

- Fever $> 38.0^{\circ}\text{C}$ for ≥ 24 hours, or report of subjective fever lasting ≥ 24 hours, laboratory evidence of inflammation, and evidence of clinically severe illness requiring hospitalization, with multisystem (> 2) organ involvement (cardiac, renal, respiratory, hematologic, gastrointestinal, dermatologic or neurological); AND
- No alternative plausible diagnoses; AND
- Positive for current or recent SARS-CoV-2 infection by RT-PCR, serology, or antigen test; or exposure to a suspected or confirmed COVID-19 case within the 4 weeks prior to the onset of symptoms.

8.3.4.4 Cardiac and Thromboembolic Events

Cardiovascular AEs will be referred to a CV Event Adjudication Committee (Section 9.7). Only adjudicated events will be included as AESIs.

8.3.5 Medically Attended Adverse Events

Medically attended adverse events will be collected according to the time points specified in the SoA (Section 1.3).

Medically attended adverse events are defined as AEs leading to medically attended visits that were not routine visits for physical examination or vaccination, such as an emergency room visit, or an otherwise unscheduled visit to or from medical personnel (eg, a medical doctor or equivalent) for any reason. AEs, including abnormal vital signs, identified on a routine study visit will not be considered medically attended adverse events.

8.3.6 Adverse Events Based on Signs and Symptoms

All AEs spontaneously reported by the participant or care provider or reported in response to the open question from the study site staff: 'Have you/the child had any health problems since the previous visit/you were last asked?', or revealed by observation will be collected and recorded in the eCRF. When collecting AEs, the recording of diagnoses is preferred (when possible) to recording a list of signs and symptoms. However, if a diagnosis is known and there are other signs or symptoms that are not generally part of the diagnosis, the diagnosis and each sign or symptom will be recorded separately.

8.3.7 Adverse Events Based on Examinations and Tests

The results from the CSP mandated laboratory tests and vital signs will be summarized in the CSR.

Deterioration as compared to baseline in protocol-mandated safety assessments should therefore only be reported as AEs if they fulfill any of the SAE criteria, are the reason for discontinuation of treatment with the investigational product or are considered to be clinically relevant as judged by the Investigator (which may include, but are not limited to, consideration as to whether treatment or non-planned visits were required or other action was taken with the study intervention, eg, dose adjustment or drug interruption).

If deterioration in a laboratory value/vital sign is associated with clinical signs and symptoms, the sign or symptom will be reported as an AE and the associated laboratory result/vital sign will be considered as additional information. Wherever possible the reporting Investigator uses the clinical, rather than the laboratory term (eg, anemia versus low hemoglobin value). In the absence of clinical signs or symptoms, clinically relevant deteriorations in non-mandated parameters should be reported as AE(s).

Any new or aggravated clinically relevant abnormal medical finding at a physical examination as compared with the baseline assessment will be reported as an AE unless unequivocally related to the disease under study.

8.3.8 Hy's Law

Cases where a participant shows elevations in liver biochemistry may require further evaluation and occurrences of AST or ALT $\geq 3 \times$ ULN together with TBL $\geq 2 \times$ ULN *and* confirmed as a Hy's Law (HL) case should be reported as SAEs.

Occurrences of AST or ALT $\geq 3 \times$ ULN together with TBL $\geq 2 \times$ ULN, where no other reason, other than the IMP, can be found to explain the combination of increases, eg, elevated ALP indicating cholestasis, viral hepatitis, another drug should be evaluated. The elevation in transaminases must precede or be coincident with (ie, on the same day) the elevation in TBL, but there is no specified timeframe within which the elevations in transaminases and TBL must occur.

Please refer to [Appendix D](#) for further instruction on cases of increases in liver biochemistry and evaluation of HL.

8.3.9 Reporting of Serious Adverse Events

All SAEs have to be reported, whether or not considered causally related to the investigational product, or to the study procedure(s). All SAEs will be recorded in the eCRF.

If any SAE occurs in the course of the study, Investigators or other site personnel will inform the appropriate AstraZeneca representatives within one day ie, immediately but **no later than 24 hours** of when he or she becomes aware of it.

The designated AstraZeneca representative will work with the Investigator to ensure that all the necessary information is provided to the AstraZeneca Patient Safety data entry site **within one calendar day** of initial receipt for fatal and life-threatening events **and within 5 calendar days** of initial receipt for all other SAEs.

For fatal or life-threatening AEs where important or relevant information is missing, active follow-up will be undertaken immediately. Investigators or other site personnel will inform AstraZeneca representatives of any follow-up information on a previously reported SAE within one calendar day, ie, immediately but **no later than 24 hours** of when he or she becomes aware of it.

Once the Investigators or other site personnel indicate an AE is serious in the EDC system, an automated email alert is sent to the designated AstraZeneca representative.

If the EDC system is not available, then the Investigator or other study site staff reports a SAE to the appropriate AstraZeneca representative by telephone.

The AstraZeneca representative will advise the Investigator/study site staff how to proceed.

For further guidance on the definition of a SAE, see [Appendix B](#).

The reference document for definition of expectedness/listedness is the IB for AZD7442.

8.3.10 Pregnancy

All pregnancies and outcomes of pregnancy should be reported to AstraZeneca except when the pregnancy is discovered before the study participant has received any IMP.

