1.3 Schedule of Activities

Table 1 summarizes the SoA at screening for all participants. **Table 2** and **Table 3** summarize the SoA during the main study for neonates (modified sample collection) and non-neonates, respectively.

Table 1 Schedule of Activities: Screening Period (All Participants)

Procedure/study day	Day -7 to Day 1 ^a	For details, see section:
Informed consent/assent	X	5.1
Assignment SID number ^b	X	6.3
Demographics and risk categorization	X	5.1
Medical history	X	NA
Complete physical examination, including height and weight	X	8.2.1
Vital signs (including pulse oximetry)	X	8.2.2
Triple 12-lead ECG	X	8.2.3
Serum chemistry, hematology, urinalysis ^c	X	8.2.4

Table 1 Schedule of Activities: Screening Period (All Participants)

Procedure/study day	Day -7 to Day 1 ^a		For details, see section:
Coagulation	X		8.2.4
Urine pregnancy test (post-pubertal females only) ^d	X		8.2.4.5
Assessment of SAEs	X		8.3
Concomitant medications	X		6.5
Serum sample for SARS-CoV-2 serology (anti-nucleocapsid) testing (all participants other than neonates)	X		8.5.3.2
Verify eligibility criteria	X		5.1, 5.2
Screening criteria specific to each cohort	Cohort 1 Pre-exposure prophylaxis	Cohorts 2 and 3 Treatment of COVID-19	For details, see section:
Documented SARS-CoV-2 RT-PCR test taken \leq 3 days before Day 1 ^c OR Rapid SARS-CoV-2 antigen test (for assignment to study cohorts) per local standard of care authorized for screening or diagnosis	X (negative)	X (positive)	8.6.1
COVID-19 Symptom screen	NA	X (Yes)	5.1

^a Screening activities may be collected over more than one visit during the 7-day screening window if necessary; if screening and dosing occur at the same visit, only one evaluation is required, unless otherwise specified. The sample taken closest to dosing and prior to dosing is considered the baseline sample.

^b Assigned by the IRT system. See Section [6.3](#) for further information.

^c Collection of urine samples for urinalysis from participants who are unable to provide urine samples is not mandatory provided that a reasonable attempt has been made to collect the samples.

^d If urine tests positive or is indeterminate, a quantitative serum β -hCG will be performed for confirmation before the participant is enrolled in the study. Pregnancy testing is for baseline purposes only, and a participant with a positive urine pregnancy test can still participate in the study.

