^d A pregnancy test at Day 1 is not required if already done and results received during the Screening Period (Day -7 to Day 1). If urine tests positive or indeterminate, a quantitative serum β-hCG will be performed for confirmation before the participant receives IMP. Pregnancy testing is for baseline purposes only, and a participant with a positive urine pregnancy test can still participate in the study.

- e The type of sample (eg, saliva, blood, nasopharyngeal) should be consistent between all study visits for each participant, but particularly for the samples collected on Day 1 and Day 8 which will be used to estimate the change in viral load. For participants in cohort 1 that have COVID-19 qualifying symptoms ([Table 13](#)) at any time during the study, an unscheduled sample will be collected for SARS-CoV-2 RT-PCR to confirm the participant is SARS-CoV-2 positive (Section [8.1.1](#)).
- f Baseline sample, not a screening sample; results not needed prior to dosing.
- g All participants will have a sample collected for SARS-CoV-2 RT-PCR on Day 1. Only Cohorts 2 and 3 (treatment arms) will have a sample collected for quantitative RT-PCR on Day 1 and Day 8. For RT-PCR, the central laboratory should be used.
- h For participants who receive AZD7442 via an IV infusion, a serum sample should be taken at the end of the infusion (and from the opposite side to the one used for the infusion).
- i The first 2 participants aged \geq 2 years to < 18 years in Cohort 1 (Sentinel Cohort) will undergo internal safety monitoring for 24 hours post IMP administration (including injection/infusion site reactions and other hypersensitivity or adverse reactions). Once the 24 h safety data review of the Sentinel Cohort is complete, recruitment can start in the remaining pediatric participants. All other participants will be monitored on site for general safety, including injection/infusion site reactions and other hypersensitivity reactions, for at least one hour after IMP administration (Section [8.3.1](#)).
- j For the first 4 days after IMP administration, the sentinel participants (2 participants aged \geq 2 to < 18 years) will be contacted daily for safety monitoring followed by weekly contact. All other participants will be contacted weekly starting from the time of IMP administration. During weekly contact the Investigator will enquire about any AEs, SAEs, MAAEs, and AESIs as well as any COVID-19 symptoms from the past 7 days.

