8.3.10.1 Maternal Exposure

Pregnancy itself is not regarded as an AE unless there is a suspicion that the IMP under study may have interfered with the effectiveness of a contraceptive medication. Congenital anomalies/birth defects and spontaneous miscarriages should be reported and handled as SAEs. Elective abortions without complications should not be handled as AEs. The outcome of all pregnancies (spontaneous miscarriage, elective termination, ectopic pregnancy, normal birth or congenital anomaly/birth defect) should be followed up and documented even if the participant was discontinued from the study.

If any pregnancy occurs in the course of the study, then the Investigator or other site personnel informs the appropriate AstraZeneca representatives within **1 day**, ie, immediately but **no later than 24 hours** of when he or she becomes aware of it.

The designated AstraZeneca representative works with the Investigator to ensure that all relevant information is provided to the AstraZeneca Patient Safety data entry site **within 1 or 5 calendar days** for SAEs (see Section [8.3.9](#)) and **within 30 days** for all other pregnancies.

The same timelines apply when outcome information is available.

The PREGREP module in the eCRF is used to report the pregnancy and the paper-based PREGOUT module is used to report the outcome of the pregnancy.

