5.1 Inclusion Criteria, 5.2 Exclusion Criteria, 5.3 Lifestyle Considerations, 8.2.4.5 Pregnancy Testing, 8.3.10 Pregnancy	Screening (Day -7 to Day 1) and Day 1 and added clarifying note; removed inclusion criterion and restrictions on females and males who are sexually active and who do not use contraception, and criterion excluding pregnant or breastfeeding females and other related text throughout the CSP.	Pregnancy: AZD7442 (EVUSHIELD™) is approved or authorized for early access/emergency use in several markets worldwide. There is no requirement to use contraception in women of child bearing potential. In a tissue cross-reactivity study with tixagevimab and cilgavimab using human fetal tissues, no binding was detected. No signals pertinent to development and reproductive toxicology have been seen in the pivotal toxicology study in nonhuman primates. EVUSHIELD should only be used during pregnancy if the potential benefit outweighs the potential risk for the mother and the fetus. Breastfeeding: The developmental and health benefits of breastfeeding should be considered along with the mother's clinical need for EVUSHIELD. AZD7442 is a combination of 2 human mAbs with nonoverlapping epitopes directed against the receptor binding domain of the SARS-CoV-2 S protein for neutralization of the virus with neither mAb having any human target. There are no potential risks based on mechanism of action.
1.3 Schedule of Activities Tables 1 and 3, 5.2 Exclusion Criteria, 5.3 Lifestyle Considerations, 6.5 Concomitant Therapy, 8.2.4 Clinical Safety Laboratory Assessments	Removed urine drug and alcohol screening, and updated the related exclusion criterion and restrictions.	Removed the urine drug and alcohol screening test as it does not provide sufficient information on chronic drug and alcohol use. Investigator assessment of the participant is sufficient for ensuring the participants do not have a history of drug or alcohol abuse that would compromise their ability to comply with study requirements as well as affect PK and safety.
1.3 Schedule of Activities Tables 1, 2, and 3	Urine collection requirement updated so that while collection should still be attempted, it is not mandatory, and clarified follow-up call language.	While there should be a reasonable attempt to collect a urine sample from participants, it is not a mandatory sample collection for any participant who is unable to provide a urine sample. The phone call language has been updated for clarification.

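### Section 8.3.10 exempts pregnancies known before dosing from sponsor reporting, although such participants may be dosed, and this conflicts with Section 8.3.10.1

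*Protocol*

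**What the plan says.** **Reporting.** Protocol Section 8.3.10 sets the general duty: "All pregnancies and outcomes of pregnancy should be reported to AstraZeneca". It then makes one exception: "except when the pregnancy is discovered before the study participant has received any IMP".

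**Eligibility.** Table 3, footnote d, in the Schedule of Activities (Section 1.3) states: "Pregnancy testing is for baseline purposes only, and a participant with a positive urine pregnancy test can still participate in the study". Footnote d of Table 1 says the same for the screening visit. Section 5.2 contains no pregnancy criterion. As background, the Version 4.0 entry in Appendix H records the removal of the "criterion excluding pregnant or breastfeeding females and other related text throughout the CSP".

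**Timing of tests.** Pregnancy is tested at screening or on Day 1 before the dose, and at no later visit. If the urine result is positive or indeterminate, a serum test "will be performed for confirmation before the participant receives IMP" (Table 3, footnote d).

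**Maternal exposure.** Section 8.3.10.1 starts the 24-hour report with the condition "If any pregnancy occurs in the course of the study". The same section says: "The outcome of all pregnancies (spontaneous miscarriage, elective termination, ectopic pregnancy, normal birth or congenital anomaly/birth defect) should be followed up and documented". It also makes congenital anomalies and spontaneous miscarriages SAEs. Section 8.3.9 requires every SAE to be reported.

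**The concern.** An exception for pregnancies found before dosing makes sense when such a finding keeps the participant out of the study, because no exposure follows. Under the current protocol a participant can be known to be pregnant, receive AZD7442 and be followed for a year. The exception was not limited to participants who are never dosed, so on its wording it takes in pregnancies whose exposure is certain from Day 1. A pregnancy discovered a week after dosing has to be reported within 24 hours; one discovered the day before dosing does not.

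What is at stake is the completeness of the sponsor's safety record in a first pediatric study. A site that follows Section 8.3.10 literally files neither the pregnancy report (PREGREP) nor the outcome report (PREGOUT). A site that follows the outcome sentence in Section 8.3.10.1 documents the outcome. What reaches the sponsor then depends on which sentence a site applies.

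**Working it through.** No arithmetic bears on the main point. The check follows one hypothetical participant whose baseline test is positive and who is then dosed.

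1. **Can she be dosed?** Yes. Footnote d of Tables 1 and 3 allows participation, and Section 5.2 has no criterion against it. The individual stopping rules in Section 7.4.1 withhold IMP only for withdrawn consent or failed eligibility. Section 6.3 says all eligible participants receive AZD7442.
2. **Does the exception apply to her?** Yes. Her pregnancy was found before any IMP, and the exception carries no condition about what happens next. Since all scheduled tests are pre-dose, this is true of every pregnancy the scheduled tests detect.
3. **Does the 24-hour trigger in Section 8.3.10.1 bring her back in?** Not clearly. It speaks of a pregnancy occurring during the study, and hers was present before dosing.
4. **What is required for each event?**

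| Event in this participant | Pregnancy report under 8.3.10 | Outcome sentence in 8.3.10.1 | SAE route |
|---|---|---|---|
| The pregnancy itself | Exempt | Not addressed | None; pregnancy is generally not an AE |
| Normal birth | Exempt | Follow up and document | None |
| Elective termination without complications | Exempt | Follow up and document | None; not handled as an AE |
| Ectopic pregnancy | Exempt | Follow up and document | Not named; depends on the general criteria in Appendix B 2 |
| Spontaneous miscarriage | Exempt | Follow up and document | SAE, reported under 8.3.9 |
| Congenital anomaly | Exempt | Follow up and document | SAE, reported under 8.3.9 |

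The second and third columns conflict for every outcome. The last column closes the gap for miscarriages and congenital anomalies, but not for the pregnancy itself, a normal birth or an uncomplicated elective termination.

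5. **Comparison within the protocol.** Section 8.3.10.2 sends the pregnancy of a male participant's partner, who received no IMP, through the pregnancy form with outcome follow-up, subject to her consent. The dosed participant in this example has no such clear route.
6. **How many could be affected?** SAP Section 2 gives a full analysis set of 46 participants, of all ages. The adolescent row of Protocol Table 5 also adds to 46 (6 + 4 + 6 + 4 + 4 + 22), but that is a planned minimum for both sexes and is unrelated to the actual total. Only post-pubertal females are tested. The documents do not say how many of them were dosed or whether any tested positive.

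**The case against.** The strongest objection is to a wider reading. A reader might infer that pregnancies exposed at dosing are neither reported nor followed. The documents do not support that. Section 8.3.10.1 asks for the outcome of all pregnancies to be followed up and documented, names normal birth and elective termination among them, and does not repeat the exception. One could argue that the exception in the parent section governs the subsection, but the text does not say so. The finding is a conflict, and it falls short of a complete absence of follow-up.

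A reader might also infer that the number of exposed pregnancies would be lost. That does not follow either. The baseline test is a scheduled procedure and dosing is recorded, so positive tests in dosed participants should be recoverable from study records. Nor can it be said that an outcome rate is lost, since with so few possible cases no informative rate would exist even under full reporting.

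Further points stand. The most serious named outcomes already reach the sponsor as SAEs. No PK or PD endpoint and no analysis set depends on this text, and the SAP plans no pregnancy listing or summary. Enrolment has stopped, so rewording changes nothing about who is dosed.

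What the objection does not remove is the exception itself. Read literally, it releases the site from notifying the sponsor of a known exposure in pregnancy and of its non-serious outcomes.

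**Conclusion.** The point holds as an unreconciled conflict in the safety-reporting text. Section 8.3.10 exempts the pregnancies that the protocol's own tests detect, footnote d lets those participants be dosed, and Section 8.3.10.1 asks for follow-up of every pregnancy outcome while its reporting trigger does not clearly reach a pregnancy already present. The gap is limited to sponsor notification of the exposed pregnancy and of outcomes that are not SAEs.

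The number affected is unknown and may be zero. If a range is wanted, 0 to 2 participants is an assumption and not a figure from the documents; each would mean one pregnancy report and one outcome report not required under Section 8.3.10. The conclusion rests on reading the exception as written, with no unstated limit to participants who are never dosed. It takes no position on whether pregnant participants should be dosed.

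**What to change.** Reconcile footnote d of Tables 1 and 3 with Sections 8.3.10 and 8.3.10.1:

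- **Section 8.3.10:** limit the exception to participants who do not subsequently receive IMP.
- **Section 8.3.10.1:** extend the reporting trigger to any pregnancy present at dosing or occurring after it, using the existing PREGREP and PREGOUT modules and the existing timelines.
- **Participants already dosed:** because enrolment has stopped, this is the most useful step in practice. Review the baseline pregnancy tests of all dosed post-pubertal females, enter any positive case retrospectively, and obtain its outcome.

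The cost is small: a clarification to the two sections or a letter to investigators (a route that Appendix A 5 foresees for safety issues), and one look through existing test results. It needs no new form, visit, sample or clinical rule.
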